1.0 INTRODUCTION

1.1 Background

Young adult cancer survivors (YACS) are particularly vulnerable to treatment late-effects including insomnia.¹⁻⁸ Insomnia is often viewed “as a temporary reaction to the cancer diagnosis or treatment,”⁹ with few long-term consequences, but insomnia frequently develops into a debilitating chronic condition. As many as 1 in 4 YACS experience significant insomnia even many years after cancer treatment.^{5-7, 10} Chronic insomnia is associated with significant health problems, including heart disease, obesity, hypertension, diabetes, depression, and anxiety.¹¹⁻²⁰ Because of their cancer treatments, YACS are already vulnerable to many of these health conditions, making access to effective insomnia treatment critically important to their overall health.²¹⁻²³

Cognitive-behavioral therapy for insomnia (CBTI) is a well-established and empirically supported treatment. Multiple randomized trials have demonstrated it is the most effective long-term insomnia treatment, even compared to pharmacotherapy.²⁴⁻²⁶ A review of CBTI for cancer survivors similarly concluded it “provides significant, lasting improvement.”²⁷ Unfortunately, despite compelling evidence, this empirically validated treatment is largely unavailable to the growing population of YACS who need it.^{28, 29} To make CBTI widely available to YACS, several barriers need to be resolved, including the shortage of trained CBTI providers,^{30, 31} the high burden of standard CBTI regimens,^{32, 33} and the lack of CBTI interventions specifically targeting the needs of YACS. Moreover, as the ongoing COVID-19 pandemic presents considerable health risk for cancer survivors,³⁴ it is imperative CBTI be delivered using methods that minimize risk of exposure.

To address these challenges and deliver effective insomnia treatment to YACS, we have developed the Sleep Treatment Education Program for Young Adult Cancer Survivors (STEP-YA), a brief low-intensity intervention presenting essential elements of CBTI in an online educational format. Delivered in a 90-minute, 1 on 1, instructor-led session, STEP-YA educates YACS about causes of insomnia after cancer, including developmental, social, and health factors affecting YACS, and introduces them to CBTI principles and methods. Following a self-management approach, the instructor provides guided behavioral planning encouraging survivors to develop an individualized sleep action plan they will implement after the session. STEP-YA

targets YACS' specific needs and experiences and supports their autonomy by helping them make informed choices to manage their own insomnia.³⁵

STEP-YA builds on our previous work successfully developing novel CBTI interventions for cancer survivors, including brief educational interventions, synchronous and asynchronous online interventions, and targeted interventions for YACS.³⁶⁻³⁹ Based on results showing low-intensity CBTI interventions are potent enough to significantly improve insomnia in cancer survivors, we have developed STEP-YA to meet the needs of the majority of YACS with insomnia for whom standard CBTI is not appealing, not available, or not needed. Guided by the ORBIT model^{40, 41} for development and early testing of behavioral interventions, we now plan this Phase I/II optimization trial (cites) to refine and preliminarily test the STEP-YA intervention.

1.2 Overview

This study will evaluate STEP-YA in an RCT of 74 off-treatment YACS (ages 20-39). As individualized coaching is an effective component of behavioral interventions for cancer survivors and other populations,⁴²⁻⁴⁴ we are interested in evaluating their utility for supporting STEP-YA outcomes. Study participants will be assigned (1:1) to receive the STEP-YA intervention either, 1) alone (non-coaching condition), or 2) with the addition of 2 remote coaching sessions (coaching condition). STEP-YA sessions will be delivered online using the Zoom platform, which is currently in use at DFCI for virtual patient visits and education programs. Participants will complete measures of insomnia and mood at baseline and again at 4- and 8-weeks post-baseline. A repeated-measures design, with each subject acting as their own control, enables the trial to efficiently evaluate potential efficacy of STEP-YA (phase IIa “proof of concept” objective). Randomization to a coaching condition makes it possible to evaluate utility of remote coaching to improve STEP-YA outcomes (phase Ib objective). As coaching sessions add significantly to costs and complexity, a goal of this study is to determine if they have potential to augment STEP-YA effects before including them in any future Phase III efficacy trials of STEP-YA.

2.0 AIMS

1. To test the hypothesis that STEP-YA improves insomnia symptoms (primary outcome) and mood (secondary outcome) in young adult cancer survivors.
2. To determine if improvement in these outcomes are superior in the coaching condition compared to the non-coaching condition.

A secondary aim will be to explore participant factors associated with clinically significant response to the STEP-YA intervention.

3.0 PATIENT SELECTION

3.1 Eligibility Criteria

To be determined by patient self-report from eligibility screening with potential participants. (See Appendix A for eligibility screening materials). Participants must be screened for eligibility ≤ 2 weeks prior to study enrollment. Participants who are screened earlier must be rescreened within this period. ISI scores are valid for 4 weeks, only rescreen with ISI if > 4 weeks since initial screening.

- Age 20-39
- History of a cancer diagnosis (except non-melanoma skin cancer) ≥ 1 year prior
- No active cancer therapy (excluding chemoprevention) in the past four months, and no further therapy planned
- Significant insomnia as evidenced by an Insomnia Severity Index score ≥ 12
- Able to read and write in English

3.2 Exclusion Criteria

- Survivors who report ever being diagnosed with Bipolar Disorder.
- Survivors who report ever being diagnosed with a Seizure Disorder or have experienced a seizure in the past 12 months.

- Intention to adjust (decrease or increase) use of any prescribed or over-the-counter medications taken to decrease insomnia during the study period.
- Survivors who report being diagnosed with sleep apnea who are not receiving recommended medical treatment for their sleep apnea (as assessed by screening questions, see Appendix A).
- Survivors who report suspected sleep apnea who have not completed an evaluation by a sleep specialist (as assessed by screening questions, see Appendix A).
- Survivors who report their usual bedtime does not fall between 5:00 pm and 5:00 am.
- Employment that involves irregular sleep patterns, such as shift-work or frequent long-distance travel across time zones, or employment in a position that could impact public safety (such as air traffic-controller, operating heavy machinery)
- Any impairment (e.g., hearing, visual, cognitive) that interferes with the ability to complete all study procedures independently.
- Prior participation in a research study which provided an educational or behavioral intervention for insomnia
- Prior participation in a behavioral treatment or patient education program for insomnia delivered at the Dana-Farber Cancer Institute, or at Boston Children's Hospital.
- Participation in behavioral or educational interventions for insomnia in the 2 years prior to enrollment. This includes in-person as well as synchronous and asynchronous online insomnia programs, but not independent use of books, workbooks or other written self-help materials addressing insomnia.

4.0 RECRUITMENT

This study will follow procedures currently in place for other survivorship interventions which recruit from multiple clinics at DFCI (17-515, 17-402) in order to identify potentially eligible survivors for recruitment purposes. Recruitment procedures for this study are identical to [name] recently approved study testing a version of the Sleep Treatment Education Program

for older survivors (DFCI 20-516). All procedures have been developed in consultation with the disease centers and have proven to be effective and non-burdensome for clinicians and patients, while ensuring that only survivors appropriate for recruitment are approached.

[name] will work with each participating clinic's leadership to determine how each clinic wishes to make their patients aware of the study, and develop specific procedures for each clinic or disease center. As in our past studies, the survivorship research coordinator will typically function in the same manner as the clinic's research coordinators, working with the clinicians to determine appropriate patients and timing for providing study information to potential participants. Additionally, each clinic will determine an appropriate clinician or clinicians to co-sign the recruitment letter/email, as seen in the recruitment materials provided in Appendix A.

After getting permission to approach potential subjects from their medical provider, subjects will be approached, screened for eligibility, and recruited by a member of the study staff.

Recruitment materials and a study information sheet can be found in Appendix A. While this could occur in person at a scheduled clinic visit, as survivorship visits are frequently conducted as telehealth visits, it is anticipated that some survivors will be contacted by telephone, videoconference, email, or mail. Templates for all of these recruitment methods can be found in Appendix A.

Eligible survivors will also be identified from Project REACH (DFCI 07-134; [name], PI), a cohort study of survivors followed at DFCI. Project REACH participants complete annual surveys of physical and emotional health and have consented to these surveys being used to determine eligibility for other survivorship studies.

To identify eligible participants, we will work directly with the administrative and clinical staff in participating clinics and programs, and we will also use administrative data sources including EPIC, OncDRS, and CORIS. We are requesting a Waiver of Authorization to identify eligible participants. Subjects will be screened in person, by telephone, or videoconference using the eligibility screen, including the ISI scale (see Appendix A).

Potential subjects may also be referred by a Dana-Farber clinician or self-refer to the study. To ensure that potentially interested YACS are aware of the study, investigators will collaborate with survivorship education and support programs both affiliated with DFCI, and those in the community. Specifically, these programs will be asked to inform their members about the study;

a brief advertisement suitable for use in patient newsletters, advocacy group newsletters or websites can be found in Appendix A. Similarly, as social media has been found to be a highly successful recruitment tool for YA cancer survivors, we will utilize social media popular with this cohort (e.g. Reddit, Facebook, Twitter, IG); a sample social media post can be found in Appendix A. A study website (STEPforSleep.com) will contain IRB-approved information about the study including contact information for the study team, the study information sheet, a link to the study on Clinical Trials.gov, and the video advertisement (see Appendix A). The study will also have a Facebook page, as well as Instagram and Twitter accounts which will direct potential subjects to the study web site. To promote the study to potentially interested cancer survivors, study staff will periodically post on these sites (see Appendix A for sample posts).

5.0 STUDY DESIGN AND METHODS

5.1 Study Design

This study is a randomized controlled trial of 74 young adult cancer survivors with clinically significant symptoms of insomnia, randomized to the STEP-YA intervention with or without 2 remote coaching sessions. All participants will take part in a single STEP-YA session, during which they will complete baseline measures prior to receiving the STEP-YA intervention. Following the intervention session, they will be randomized to the coaching or non-coaching conditions. Participants will complete follow-up measures 4 and 8 weeks post-baseline.

5.2 Methods

See section 5.5 for descriptions of all study measures. Copies of the assessments can be found in Appendix B, and participant correspondence in Appendix C.

Informed Consent: We are requesting a Waiver of Documentation of Informed Consent for this study, as it is a minimal risk study involving no procedures (questionnaires and educational session) for which signed consent is generally required outside of the research context. The intervention sessions in this study are similar to educational sessions currently conducted through the Blum Center at DFCI, and for which no signed consent is required. A similar online intervention currently being conducted by [name] (17-515) was granted a waiver of documentation of consent, and we propose to utilize those approved consent procedures for this

study. Potential participants will be provided with a study information sheet which contains all the elements of informed consent (See Appendix A), and will have a consent conversation with a member of the study staff in which they can ask questions about the study or study procedures before providing verbal consent. As it is anticipated that many off-treatment survivors will not have in person clinic visits at DFCI for the foreseeable future, it is expected that most of these consent conversations will take place by telephone or videoconference, although they could be in person if requested.

Intervention session: After expressing interest, participants will be scheduled for an individual videoconference intervention session. The intervention session consists of the following components:

- 1) Informed Consent: Study staff will review the study procedures and the Study Information Sheet with the participant and answer any questions they may have. They will then obtain verbal consent. (Verbal consent procedures can be found in Appendix C)
- 2) Baseline measures: Study staff guide participants in completing baseline measures including insomnia and mood using the Qualtrics web-based survey platform.⁴⁵ Participants enter data directly into the system, and the study staff do not collect data from participants.
- 3) Intervention Delivery. After completing baseline measures, the participant will immediately receive the STEP-YA intervention session via videoconference. (See section 5.3 for a description of the STEP-YA intervention). During the session, both the participant and the interventionist will be blinded to whether the participant has been randomized to receive the coaching sessions.
- 4) Randomization: After completing the session, randomization will be performed using Sealed Envelope, a commercially available online software application for randomising patients into clinical trials. Participants will be randomized (1:1) to either: **1)** STEP-YA alone (non-coaching condition) or **2)** STEP-YA with the addition of 2 remote coaching sessions (coaching condition). Participants will then be informed of whether they were randomized to receive the coaching sessions, and will schedule their first telephone call (first coaching session for those in the coaching condition or 4-week follow-up for those in the non-coaching condition). Additionally, participants will be asked to provide preferences for all future contact and correspondence (i.e., phone, email, send secure, text, mail) and

these preferences and addresses/phone numbers will be recorded in the participant's record.

- 5) Session evaluation: Participants will receive a link to a questionnaire on which they will report on ease of use and acceptability, satisfaction, and credibility of the session. To promote completion of the questionnaire, participants will be encouraged to complete it while still in the Zoom session, but can choose to complete it at a later time. Participants will receive a \$10 gift card upon completion of this evaluation.

Coaching Sessions: Participants randomized to the coaching condition will receive 2 individualized remote coaching sessions 1, and again 2 weeks following their STEP-YA session. (See section 5.4 below for a description of the coaching sessions and timing).

Post-intervention Follow-up: At 4- and 8-weeks post-baseline, study staff will recontact participants by telephone at previously scheduled times, ask them to enter follow-up data directly into Qualtrics, and provide technical assistance if needed. Participants who cannot complete the full assessment at that time due to time constraints will be asked to complete the 7-item ISI (primary outcome measure) verbally and their responses will be collected; they will then be asked to complete the full questionnaire at their earliest convenience. Participants will receive emailed reminders in advance of each phone call. At the 4-week call, participants will schedule a phone call for the 8-week assessment.

Incentive: Participants will receive a \$25 Amazon gift card upon completion of each follow-up assessment.

Optional 16-week ISI: At the time of their 8-week follow-up phone call, participants will be asked if they would be willing to complete an additional sleep checklist two months later. Participants who agree will receive a Qualtrics link to the 7-item ISI 8 weeks later by email. This would take approximately 1-2 minutes to complete, and participants will not receive an incentive for this optional checklist. The link would be sent again a week later for non-responders, but participants will receive no additional reminders.

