Intervention Evaluations: Participants will complete evaluations at several timepoints. 1) At the end of the intervention session, participants will report on ease of use and acceptability using checklist items adapted from the Telehealth Usability Questionnaire⁶⁶ and satisfaction will be assessed with checklist items adapted from [name] previous survivorship education trials. 2) Participants who are randomized to the coaching condition will complete a brief satisfaction evaluation of the coaching sessions after the second coaching phone call. 3) All participants will complete a brief questionnaire to provide their feedback about the intervention and how it could be improved at the 8-week post-intervention timepoint.

Steps to insure complete data: Participants will complete baseline measures online using Qualtrics at the intervention session prior to randomization to insure completeness. Following procedures found to be effective in [name] DFCI protocols 17-515, 15-336 and 14-583, the study also makes use of scheduled telephone appointments to insure timely completion of the follow-up assessments. In previous intervention studies, telephone appointments have been highly effective for encouraging survivors to complete assessments; we have achieved 100% complete data for primary endpoints and 95% complete data overall using this method.

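### Participants are told their arm before they rate the STEP-YA session, so reaction to the assignment could influence ratings of a session that is the same in both arms

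*Combined protocol and SAP*

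**What the plan says.** Section 5.2 (Methods, Intervention session) numbers the parts of the session.

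- **Step 3, delivery.** While STEP-YA is being given, "both the participant and the interventionist will be blinded to whether the participant has been randomized" to coaching.
- **Step 4, randomization and disclosure.** "After completing the session, randomization will be performed using Sealed Envelope", and then "Participants will then be informed of whether they were randomized to receive the coaching sessions". In the same step the participant books either a first coaching call or the 4-week follow-up call and gives contact preferences.
- **Step 5, session evaluation.** The participant receives a questionnaire link on which "they will report on ease of use and acceptability, satisfaction, and credibility of the session". Staff encourage completion while the Zoom call is still open, and a $10 gift card follows completion. The participant may decline to do it then ("but can choose to complete it at a later time"), and no time limit is stated.

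Section 5.1 agrees that allocation comes after delivery: "Following the intervention session, they will be randomized to the coaching or non-coaching conditions". Section 5.5 (Intervention Evaluations) describes the same form: "At the end of the intervention session, participants will report on ease of use and acceptability". It adds satisfaction, does not list credibility, and does not mention disclosure.

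Section 7 names the 8-week change in ISI as the primary endpoint and the 8-week change in POMS-SF as the secondary endpoint. It contains no analysis of the session ratings.

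**The concern.** The two arms differ only in what follows the STEP-YA session. The plan conceals the arm while the session is delivered, then lifts that concealment before asking how the session was received. The items are subjective and self-reported. A participant who has just learned whether coaching will follow may rate the session, or decide whether to complete the form, partly in response to that news.

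The introduction presents the study as an optimization trial meant to refine STEP-YA and test it preliminarily. The step 5 form is the most immediate record of how acceptable the session was, and the only place where the plan mentions credibility. Coaching has its own satisfaction form after the second call, so the step 5 form is the one meant to describe the session alone. If its ratings differed by arm, the investigators could not tell a reaction to allocation from chance or from a real difference in how the session was received.

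**Working it through.** No figure in the plan bears on this point, so the check is a comparison of the sections, followed by a short algebraic argument about what can and cannot be said on size.

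**1. Is the arm known when the rating is requested?**

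| Source | Randomization | Disclosure | Session rating |
|---|---|---|---|
| Section 5.1 | after the session | not stated | not stated |
| Section 5.2, steps 3 to 5 | step 4, after delivery | step 4 | step 5 |
| Section 5.5 | not stated | not stated | end of the session |
| Section 7 | immediately after baseline | not stated | not mentioned |

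Only Section 5.2 states when the participant is told the arm, and it puts the rating afterwards. Section 5.5 does not contradict this. Section 5.2 counts randomization and the evaluation as components of the session, so a rating at the end of the session fits step 5. Section 7 places randomization earlier than Sections 5.1 and 5.2 do. That is a separate inconsistency, and it does not alter when the participant learns the arm.

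**2. How late can the rating be?** Step 5 sets no limit. Section 5.4 allows coaching sessions between 5 and 23 days after STEP-YA. A coaching-arm participant who defers the form by 5 days or more could therefore rate the session after receiving coaching.

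**3. Can the size be derived?** Allocation is 1:1 with 74 enrolled, so about 74 / 2 = 37 participants per arm rate the session knowing their assignment. Suppose disclosure raises the mean rating by *a* in the coaching arm and lowers it by *b* in the other, with either allowed to be zero or negative. For an identical session:

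- spurious difference between arms = *a* + *b*
- shift in the pooled mean = (*a* − *b*) / 2

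If *a* = *b*, the pooled mean does not move and the arms differ by 2*a*. If only the non-coaching arm reacts (*a* = 0), the pooled mean moves by −*b*/2 and the arms differ by *b*. The documents give no value or sign for *a* or *b*, so neither result can be turned into a number.

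**4. Does anything planned depend on the ratings?**

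- Aims (Section 2.0): insomnia, mood, coaching against no coaching, and factors associated with response. None concerns session ratings.
- Endpoints (Section 7): ISI and POMS-SF change at 8 weeks.
- Power (Section 7): d = 0.52 within each arm, and d = 0.62 between arms for the primary endpoint, with 64 evaluable. Neither uses the ratings.
- Response model (Section 7): estimated from baseline variables. A rating taken after the session is not one.

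**The case against.** The strongest case against is that little rests on these ratings. No aim, endpoint, power statement or planned analysis uses them, and the plan proposes no comparison of them between arms. Section 5.5 also schedules an 8-week questionnaire for all participants on the intervention and how to improve it. That form serves refinement directly and does not depend on the order of steps 4 and 5. This stands, and it makes the point minor.

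A second objection is that the direction is not obvious. Coaching may be welcome, but it is also two further contacts of about 30 minutes each, and the introduction says that standard, more intensive treatment does not appeal to many in this population. Some participants may be relieved or indifferent. This also stands.

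A third is that Sections 5.1 and 5.5, read without Section 5.2, would allow the rating to come before randomization. That is true, but Section 5.2 is the only operational sequence and it gives the opposite order.

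A reader might go further and infer that the ratings are certainly biased, both in the pooled level and between arms. The documents do not support that. They show exposure to a possible influence and give no measured effect, and opposite reactions in the two arms could leave the pooled mean unchanged. A reader might also infer that earlier ratings would supply a useful adjustment covariate. Section 7 specifies an arm-by-time analysis of variance without covariates, so the plan has no use for one.

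**Conclusion.** The point holds as an avoidable risk. As Section 5.2 is written, every participant is asked to rate an identical session, delivered with the arm concealed, after learning the assignment. The ratings could be influenced by reaction to it, by an amount and in a direction that the documents do not give.

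The effect on the trial's main results is nil: the ISI and POMS-SF endpoints, the power and the sample size do not change. What is exposed is the immediate description of acceptability, satisfaction and credibility. A reader might take the finding as a failure of blinding that threatens the efficacy results, but the plan conceals the arm only during delivery, and the ratings feed no efficacy analysis.

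The conclusion rests on staff following the numbered order of Section 5.2. If they already collect the form before disclosure, only the text needs correcting. This is a minor improvement, worth making because it is cheap.

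**What to change.** 1. In Section 5.2, send the evaluation link in the Zoom call right after delivery, then randomize and disclose the arm. The order that matters is rating before disclosure, so this holds however the difference between Section 7 and Sections 5.1 and 5.2 on randomization timing is resolved.
2. Align Section 5.5: state that the form precedes disclosure, and list credibility if it is to be measured.
3. Keep the option to defer. Use the survey completion time, set against the time of disclosure, to flag forms completed after the arm was known.
4. Report all ratings overall and by arm. Show the pre-disclosure subset as a sensitivity analysis. Making that subset the main result would restrict it to people willing to complete the form at once, which introduces selection.
5. If enrolment is too far advanced to change the order, report the ratings by arm with completion time and state the limitation.

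Cost: a few minutes' delay before randomization and call scheduling, at the end of a 90-minute session, when the participant is still needed on the call. No new instrument, visit or staff is required. The flag assumes that the online form stores a completion time; if disclosure time is not already recorded, staff would need to note it.
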